Primary data analysis will be an intent-to-treat analysis, which includes all randomized participants. Of note, every attempt will be made to continue assessing participants even if they drop out of treatment. In addition, we will replicate all analyses with the completers only. The hypothesis that The Treatment Ambassador Program will yield higher rates of ART initiation by the completion of the intervention will be tested using Fisher's exact test; the treatment effect estimate will be summarized in terms of a relative risk and 95% confidence interval. Any baseline demographic or clinical variables identified as necessary covariates in preliminary analyses will be included in a logistic regression analysis that examines the main effect of treatment condition on the rates of ART initiation.

Power/Sample Size Considerations. Because this is a pilot study, power considerations for testing null hypotheses are somewhat less relevant than having adequate degrees of freedom to estimate treatment effects with a reasonable degree of precision for potential use in a future fully-powered trial. However, for completeness, we present a summary of the power analyses for the primary hypothesis below. With a sample size of up to 45 per treatment group, the probability is greater than 80 percent that the study will detect a difference of 25% in the percent who initiate ART. This is based on the assumption that the percent who initiate ART in the control group is approximately 10%, as seen in our prior research in SA. Thus, the study is adequately powered to detect medium-to-large effect sizes (corresponding to a relative risk = 3.5) for the primary outcome. Finally, allowing for a dropout or attrition rate anticipated to not be greater than 10%, we plan to recruit a total of up to 90 participants (45 per group) to ultimately guarantee our complete sample of 80 participants. This proposed sample size provides more than sufficient degrees of freedom to obtain a precise estimate of the primary outcome event rate and a preliminary relative risk

comparison of the two treatment groups, even when allowing for up to 10% loss to follow-up. If promising results are detected, these data will provide an estimate of the reliability of the intervention effect to inform power calculations for a larger RCT.

Process Evaluation to Examine the Feasibility and Acceptability of the Intervention.

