Process evaluation analysis. We will use an inductive content analytic approach to analyze qualitative data. This approach consists of the following steps: (1) data reduction through coding, (2) category construction, (3) comparison, and (4) interpretation.

Coding. Coding will begin with a provisional start-list of themes based on prior research. Twenty percent of the interviews will be independently read and new themes iteratively generated based on identifying themes not present in the start-list, which will result in a codebook. The team members will code 20% additional interviews to calibrate the methods of evaluation, and one individual, using the standards established, will code the remaining interviews (Cohen's Kappa ≥ 0.80). For each of the seven survey measures, we will compare responses at 6 months by computing the mean response for each arm, a 95% bootstrap confidence interval for the between-arm difference in means, and a permutation test p-value for the between-arm difference in means adjusted for each participant's baseline score. To assess preliminary efficacy, rates of ART initiation at 3 months for the two arms will be

compared by computing the relative “risk” of initiation and testing for an association between arm and initiation rate using Fisher’s exact test.

We will use NVivo10[©] (QSR International Pty Ltd 2014) software to code and manage the data. The result will be a reduced data set consisting of an initial set of concepts and corresponding sections of interview/field note text -- the basis for category construction. Categories will be developed by grouping codes and coded data into meaningful clusters to form larger concepts. We will formulate labels and definitions for each new concept. Final versions of categories will include: (1) the category label or name, which should convey a category’s essential meaning; (2) the operational definition and/or an indication of the variety of specific forms the category takes; and (3) evidence of validity in the form of examples of the data from which the category was formulated. The role of interpretation here is to develop conceptual categories into larger explanations to guide process evaluations.

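### Power above 80% is stated without alpha, sidedness or method; at two-sided 0.05 the planned Fisher's exact test has about 76% at 45 per arm (72% if only 40 per arm are analysed)

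*Combined protocol and SAP*

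**What the plan says.** The primary analysis paragraph in Research Design and Methods tests the hypothesis of higher ART initiation by the end of the intervention with Fisher's exact test. It adds that "the treatment effect estimate will be summarized in terms of a relative risk and 95% confidence interval". On the analysis set it says: "Primary data analysis will be an intent-to-treat analysis, which includes all randomized participants". A completers-only replicate is also planned.

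The next paragraph, Power/Sample Size Considerations, opens its claim "With a sample size of up to 45 per treatment group" and continues that "the probability is greater than 80 percent that the study will detect a difference of 25% in the percent who initiate ART". The assumption is that "the percent who initiate ART in the control group is approximately 10" percent, and the effect is equated with a relative risk of 3.5. It concludes: "Thus, the study is adequately powered to detect medium-to-large effect sizes". It then allows for up to 10% attrition and recruits up to 90 "to ultimately guarantee our complete sample of 80 participants".

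The Coding paragraph of the process evaluation analysis describes the 3-month comparison again, as "testing for an association between arm and initiation rate using" Fisher's exact test.

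None of these places, nor any other part of the document, gives the significance level, the sidedness or the method behind the power figure.

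**The concern.** A power figure describes a particular test at a particular level. Here the test is named and the level is not, so the figure cannot be checked as written. Fisher's exact test is conservative at samples of this size. A figure taken from a large-sample formula can therefore exceed 80% while the test that will actually be run falls short.

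Two things are at stake. First, the sentence supports the statement that the study is adequately powered for a relative risk of 3.5, and a reader of a non-significant result would rely on a miss rate below 20%. Second, with sidedness undeclared, a result with a one-sided p-value between 0.025 and 0.05 could be called either way after the data are seen.

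**Working it through.** **Inputs from the plan.** Control rate p1 = 0.10. Difference 0.25, so p2 = 0.35; the relative risk of 0.35/0.10 = 3.5 confirms that the 25% is absolute. Allocation is 1:1. n = 45 per arm is the full randomized set. n = 40 per arm is the complete sample of 80; 10% attrition from 90 leaves 81.

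**Assumed, because the plan is silent.** Two-sided alpha of 0.05. The 95% confidence interval and the wording about testing an association fit this. The hypothesis itself is worded directionally, so one-sided results are also shown.

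**Step 1: reproduce the plan's figure.** Normal approximation, pooled variance under the null, no continuity correction:

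Power = Φ{ [d − 1.96·√(2·p̄·(1−p̄)/n)] / √([p1(1−p1) + p2(1−p2)]/n) }

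Here p̄ = 0.225, 2·p̄·(1−p̄) = 0.34875, and p1(1−p1) + p2(1−p2) = 0.09 + 0.2275 = 0.3175.

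- n = 45: (0.25 − 1.96 × 0.0880)/0.0840 = 0.922, so power is 82.2%.
- n = 40: (0.25 − 1.96 × 0.0934)/0.0891 = 0.752, so power is 77.4%.

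With the unpooled standard error throughout, Φ(d/SE − 1.96) gives 84.5% at 45 and 80.1% at 40. Subtracting a continuity correction of 1/n from d in the pooled formula gives 74.5% at 45. The stated figure therefore reproduces at 45 per arm, but only with an uncorrected approximation.

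**Step 2: power of the planned test.** For every pair (x, y), with x from Binomial(n, 0.10) and y from Binomial(n, 0.35), compute the Fisher p-value and sum the probabilities of all tables with p ≤ 0.05.

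| Per arm | Fisher, two-sided 0.05 | Fisher, one-sided 0.05 |
|---|---|---|
| 40 | 71.7% | 81.5% |
| 45 | 76.1% | 85.2% |
| 48 | 79.8% | not computed |
| 49 | 80.9% | not computed |

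At two-sided 0.05 the miss rate for a true 25-point effect is 100 − 76.1 = 23.9% at 45 per arm and 100 − 71.7 = 28.3% at 40.

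**Step 3: detectable difference.** With a 10% control rate and two-sided Fisher, power at 45 per arm is 79.2% for 26 points and 80.1% for 26.3 points (relative risk 36.3/10 ≈ 3.6). At 40 per arm it is 80.5% for 28 points (relative risk 38/10 = 3.8).

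**Step 4: sensitivity.** Two-sided Fisher, 45 per arm, 25-point difference held:

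| Control rate | 5% | 8% | 10% | 12% | 15% | 20% |
|---|---|---|---|---|---|---|
| Power | 86.3% | 79.7% | 76.1% | 73.1% | 69.5% | 65.9% |

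Fisher power also moves unevenly with the exact split. The same 90 people divided 44/46 or 46/44 (control/intervention) give 79.4% or 80.7%; 43/47 and 47/43 give 79.6% and 79.7%.

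**The case against.** The strongest reply is that nothing was miscalculated. The standard pooled formula at two-sided 0.05 gives 82.2%, and a one-sided 0.05 Fisher test, which the directional hypothesis might suggest, gives 85.2%. This stands in part: the defect is a missing specification and a probable mismatch between the power method and the test, not a slip in arithmetic. It does not rescue the sentence. The approximation is not the planned test, it falls to 77.4% at the plan's own complete sample, and no one-sided test is declared.

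A second reply is that the shortfall is fragile. Splits one or two away from 45/45 bring the same test to roughly 79–81%, and an 8% control rate gives 79.7%. That is correct, and the gap should not be read as sharper than it is. But 45 per group is the planned split, and a control rate above 10% moves power the other way. The plan itself expects its enhanced referral to shrink the apparent effect (Special issue #5; Ensuring access to ART).

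Third, 40 per arm is not the primary analysis set. The analysis is intent-to-treat, and initiation is also ascertained from medical and laboratory records, so a missed survey need not mean a missing outcome. This stands; the 72% figure is conditional and 76% is the main one.

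Finally, the plan calls power secondary in a pilot and sets no go/no-go rule based on significance. This also stands, and it limits the consequence to how the result is read.

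**Conclusion.** The concern holds. Alpha, sidedness and power method are not stated. At two-sided 0.05 with 45 per arm and 35% versus 10%, the planned Fisher's exact test has 76.1% power, about 4 points below the claimed minimum. It has 71.7% if only 40 per arm are analysed. Under that test, 80% needs 49 per arm.

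These figures rest on the two-sided 0.05 assumption, which the document supports but does not settle. Under one-sided 0.05 the claim would be true at both sizes (85.2% and 81.5%), but the omission would remain. The point should be fixed because the statement of adequate power is not delivered by the planned test on the conventional reading. The effect is on interpretation only; no participant protection depends on it.

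**What to change.** 1. State alpha, sidedness and the power method in Power/Sample Size Considerations, and add one line on alpha and sidedness to the primary analysis paragraph.

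2. If a two-sided 0.05 Fisher test is intended, replace the power sentence with:

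> With 45 participants per group and a two-sided Fisher's exact test at alpha 0.05, power is about 76% to detect ART initiation of 35% versus 10% (about 72% if only 40 per group are analysed). With a 10% control rate, the difference detectable with 80% power is about 26.3 percentage points at 45 per group and 28 at 40 per group.

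3. Remove or qualify the statement that the study is adequately powered.

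4. If a one-sided test was intended, declare it before outcome data are seen, both there and where the 3-month comparison is repeated under the process evaluation analysis, and label the power figure accordingly.

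The cost is a few lines of text. No extra participants or procedures are needed. If the two-sided test is kept, the published power becomes about 4 points or more less favourable.

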The primary outcome will be the proportion of individuals who start ART in the intervention arm compared with those in the control arm (standard of care is to refer to a local clinic to initiate ART). We will ascertain this through the medical record for those who start treatment on site (approximately 80-85% of testers at this site), and through the National Health Laboratory Service (N HLS) for those who start care off site. Participants will complete surveys at baseline and at the end of the intervention. After completing the pilot, we will conduct a process evaluation of a subset of the intervention group. After the process evaluation is completed, we

will use the results to revise the intervention protocol in preparation for a fully powered multi-site RCT. The progression of protocol and manual development, pilot testing for feasibility, and eventual RCT is consistent with the staged model of behavioral intervention development.²

Study Site: This study team will be based at the Desmond Tutu HIV Foundation (DTHF) Gugulethu Research Offices, based at the Gugulethu Community Health Centre. DTHF is an internationally- recognized HIV research center that has been involved in community-based research since 2002. Their testing center is based in Gugulethu (population 400,000), South Africa where 48% of residents are unemployed and 64% live on <400 SA Rand (ZAR) [approximately <US\$40] per month. The vast majority of the population uses local public sector health services that are provided free of charge. In 2012, the HIV prevalence among women attending local antenatal care services was 27%.

The intervention sessions will be conducted at one of a few local sites identified by our community staff and CAB in Gugulethu e.g. JL Zwane Church, the Gugulethu library, or at their homes. The participant may choose where he/she feels most comfortable.

Eligibility Criteria for Treatment Ambassadors (TA): TAs will be identified through leaders among a community of PLWH who are currently in care in Gugulethu.

Eligibility Criteria for Participants in the Trial:

Inclusion criteria include:

- 1) HIV-infected adults, 18 years and older, refusing to initiate ART within three to six months of learning eligibility;
- 2) ART naïve,
- 3) Live within 60 km of Hannan Crusaid clinic (due to prohibitive costs of following participants to remote locations);
- 4) English or Xhosa speaking; and
- 5) Eligible for treatment under current South Africa guidelines

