Special issue #5 - Access to ART during the study: ART usage has clearly been shown to decrease morbidity and mortality, as well as decrease heterosexual transmission of HIV. For patients who refuse ART, it is our ethical duty to ensure that access to ART is optimized, and we provide a standard of care that provides free and accessible ART. All participants will be counseled on the benefits of ART and provided with direct referrals if they meet treatment criteria. While we recognize this may impact our findings, and possibly result in our underestimating the impact of our intervention due to a Hawthorne effect in the control arm, we believe that we have an ethical obligation to ensure refusers receive proper information, referral, and access to ART during the course of the study.

Special issue #6 – *Psychological Distress*: Participants may experience psychological distress resulting from the assessment questions. Using strategies established in our previous SA and US studies, including the pilot study (NYSPI IRB # 6848), steps will be taken to minimize the risk of psychological distress resulting from assessment questions (see page 15 below)

Adequacy of Protection Against Risks:

Informed Consent: We will obtain written informed consent for all persons in this study. We do this through a process of continuous informed consent, such that research assistants will remind subjects throughout their initial intake and interview process that participation is voluntary, and they can seek to opt-out and/or speak with a counselor at any time. If there is any concern that the client is unable to give full informed consent due to anxiety, we will not pursue further questioning and discount the interview.

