Planned procedures for protecting against fatigue - Interviews will last 45-60 minutes. Regular breaks will be scheduled throughout the session. Additionally, subjects will be informed that they can take a break or stop at any time. Staff will be well-trained and supervised under the direction of experienced clinical researchers.

Discussion of sensitive topics- Efforts will be made to minimize discomfort by assuring that interviewers are well-trained and that they will inform participants beforehand about the nature of the questions and assure participants of privacy. The interviewer will be available after the interview to debrief with the participant if s/he is in any way concerned by the nature of the questions. Routine demographic questions will be asked first, followed by more personal questions. Participants will be informed that they have the right to decline participation in the study, to refuse to answer any questions, or to withdraw at any time without adverse consequences. In addition, researchers will be sensitive to any potential concerns regarding mistrust of providers. We will review all data collection materials with our community advisory board to guide our research. The CABs have helped to foster a culture of trust and mutual understanding with the community and to ensure that the research conducted through the Desmond Tutu HIV Foundation respects the values and cultural differences among those who participate. As an added level of protection for clients, we will ensure that the research assistant working on this project is not a healthcare provider on staff at the clinic.

Ensuring access to ART - We will offer “minimal wait” referrals to either medical providers or counselors at every study encounter to minimize structural barriers to ART initiation. A “minimal wait” visit means that the participant will be referred to a medical provider and/or counselor and will be the next individual seen as needed. We recognize that this enhanced referral strategy will produce a Hawthorne effect by decreasing the impact of our planned intervention. This, however, does not represent a significant change from clinic policies that are currently in place, and is consistent with the overarching philosophy of GCHC and The Desmond Tutu HIV Foundation. In addition, it fulfills our ethical obligation to provide access to lifesaving therapy, and is a conservative bias towards the null.

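### The 10% control rate behind the power statement is not shown to apply to a control arm that also receives ART counselling and minimal-wait referral

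*Combined protocol and SAP*

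**What the plan says.** **Comparator.** The Specific Aims, the primary-outcome paragraph of Research Design and Methods, and the RCT Randomization paragraph all describe the control arm as standard of care, meaning a referral for ART. In the primary-outcome paragraph: "standard of care is to refer to a local clinic to initiate ART".

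**What participants receive.** Potential Risks, Special issue #5, says: "All participants will be counseled on the benefits of ART and provided with direct referrals if they meet treatment criteria". It adds that this may affect the findings and possibly lead to underestimation through a Hawthorne effect in the control arm. Measures to Protect Against Risk, under Ensuring access to ART, offers next-in-line visits with a provider or counsellor at each study contact. It continues: "We recognize that this enhanced referral strategy will produce a Hawthorne effect by decreasing the impact of our planned intervention". The next sentence says that this "does not represent a significant change from clinic policies that are currently in place", and the paragraph ends by calling the bias conservative.

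**Power.** Power/Sample Size Considerations assumes that "the percent who initiate ART in the control group is approximately 10%, as seen in our prior research in SA". "With a sample size of up to 45 per treatment group", it states that "the probability is greater than 80 percent that the study will detect a difference of 25% in the percent who initiate ART", and describes the trial as adequately powered for "medium-to-large effect sizes (corresponding to a relative risk = 3.5) for the primary outcome". It makes no allowance for the effect expected in the risk sections and gives no range of control rates.

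**The concern.** The label in the design sections and the care described in the risk sections do not match. The contrast this trial estimates is the Treatment Ambassador Program (TAP) against referral plus ART counselling plus minimal-wait access. A report that follows the design sections would call it TAP against standard-of-care referral.

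The power paragraph inherits the problem. It takes a rate from prior research without saying what referral or counselling was in place then, while other sections expect the trial's own package to reduce the observed effect.

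Two things are at stake. One is the meaning of the stated power and of the relative risk of 3.5, both tied to the 10%. The other is the next trial. Research Design and Methods names a fully powered multi-site RCT as the next step, and the power paragraph says the pilot data may inform its power calculations. A control rate seen under one package but labelled as another could mis-size that trial.

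**Working it through.** **Inputs.** From Power/Sample Size Considerations: 45 per arm, control rate 10%, difference 25 points, hence TAP rate 35% and RR = 0.35/0.10 = 3.5. The planned test is Fisher's exact test, from the primary analysis paragraph. Alpha and sidedness are not stated; two-sided 0.05 is assumed. The documents give no control rate under the counselling and minimal-wait package, so 5% to 25% is an assumed range.

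**Step 1: reproduce the plan's figure.** Pooled normal approximation, with p̄ the mean of the two rates:

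power = Φ{[(p2 − p1) − 1.96·√(2p̄(1 − p̄)/n)] / √[p1(1 − p1)/n + p2(1 − p2)/n]}

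With p1 = 0.10, p2 = 0.35, p̄ = 0.225 and n = 45, the null standard error is 0.0880 and the alternative standard error is 0.0840. So power = Φ[(0.25 − 1.96 × 0.0880)/0.0840] = Φ(0.92) = 82.2%. The plan's claim of more than 80% reproduces. The margin is thin: the same approximation needs 43 per arm for 80%.

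**Step 2: use the planned test.** Exact Fisher power sums the binomial probabilities of all pairs of counts in 0 to 45 for which the two-sided Fisher p-value is at most 0.05. At 10% against 35% it is 76.1%. This is the reference value for the planned analysis, before the control rate is questioned.

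**Step 3: vary the control rate, keeping the 25-point difference.**

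| Control | TAP | RR | Fisher power | Normal power |
|---|---|---|---|---|
| 5% | 30% | 6.0 | 86% | 89% |
| 10% | 35% | 3.5 | 76% | 82% |
| 15% | 40% | 2.67 | 70% | 77% |
| 20% | 45% | 2.25 | 66% | 72% |
| 25% | 50% | 2.0 | 63% | 69% |

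Like for like, moving from 10% to 15% costs 76.1 − 69.5 = 6.6 points by Fisher and 82.2 − 76.6 = 5.6 points by the normal approximation. The other part of the fall from the plan's figure, 82.2 − 76.1 = 6.1 points, is the choice of test.

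**Step 4: worst case.** If the package raised the control rate only and TAP stayed at 35%, Fisher power would be 50% at a 15% control rate, 27% at 20% and 13% at 25%. This assumes no gain in the TAP arm, although both arms receive the package. It is a bound, not an expectation.

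**The case against.** The strongest reply is that the 10% may be right. The access paragraph says the referral is close to existing clinic policy. If the prior research ran under similar policies, the 10% applies as it stands. This reply stands: the documents do not describe the conditions behind the 10%, so they cannot show it to be wrong.

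A reader might go further and infer that, on the plan's own account, the control rate must exceed 10%. The documents do not support that. Special issue #5 says only that findings may be affected, the access paragraph says the intervention's impact will fall, and neither gives a rate or compares one with 10%.

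A reader might also date the 10% to the years before test-and-treat, since the Background describes earlier work in people eligible at CD4 below 350 and Recruitment Procedures cites a cohort approved in 2014. Neither is named as the source of the 10%. The direction would be open in any case: the Background says people who feel healthy often delay, so a wider eligible group could start less often. The range must therefore run both ways.

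It is also fair that this is a pilot focused on acceptability and feasibility, that power is given for completeness, and that the practice and its expected direction are disclosed twice. These points limit the consequence. They do not remove it: the power paragraph still claims adequate power, and the disclosures do not reach it or the comparator's label.

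**Conclusion.** The concern holds in a limited form. The comparator is labelled standard-of-care referral, while all participants receive counselling, direct referral and minimal-wait visits. The plan contradicts itself on whether this is enhanced care. The 10% is neither justified for this comparator nor adjusted for the effect the plan expects; it is not shown to be wrong.

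With a 25-point difference, a control rate five points above 10% costs about six points of power under either method, and one five points below raises it. The plan's figure of more than 80% holds at 10% only by the normal approximation; the planned Fisher test gives 76%. These figures rest on 45 per arm, an assumed two-sided 0.05 level and an assumed range of control rates. The figures with TAP held at 35% are a worst case and should not be read as the likely loss.

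**What to change.** 1. Under Ensuring access to ART, reconcile the statement that the referral strategy is enhanced and effect-reducing with the statement that it is not a significant change from current policy.
2. In the Specific Aims, the primary-outcome paragraph, the Randomization paragraph and the conclusions, describe the comparator by what controls receive: referral plus ART counselling and minimal-wait referral. Call it enhanced standard of care if the enhanced statement is the one kept.
3. In Power/Sample Size Considerations, name the source of the 10% and the referral and counselling in place when it was seen. State alpha and sidedness. Restate power and RR for the planned Fisher test over control rates on both sides of 10%, for example 5% to 25%. Label any case with TAP held at 35% as a worst case.
4. State that the pilot control rate will inform a larger RCT only if that RCT gives its controls the same package.

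The cost is wording and a short table. It needs no extra participants or procedures, and no change to patient care is proposed. The downside is a less favourable stated power: 76% by the planned test at the plan's own rates, and lower if the control rate is above 10%.

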Process evaluation data, integral to the development of cluster RCTs, will be collected to assess the implementation, feasibility and acceptability of the different intervention components. Using a mixed-method approach, we will collect data from qualitative and quantitative sources throughout the pilot study. Data collection will include:

Attendance registers to provide data on enrollment, dropout and attendance of the intervention. Registers will be filled out by intervention staff, beginning with the enrollment visit. Staff will collect information on training attendance and participation levels (assessed on a 1-5 scaled rubric).

Weekly meetings with detailed minutes including research staff and TAs will document challenges and problems with recruitment and study procedures. The RA will document challenges in both the intervention and control conditions, including reactions by participants, difficulties encountered, areas for improvement, and overall assessment of project implementation. Twice monthly debriefings to review these notes will occur with the intervention team and study investigators.

In-depth interviews will be conducted at two points in the study. The first time will be after completion of the open, non-randomized pilot, at which time we will interview all 10 participants (all of whom received the pilot intervention) and the Treatment Ambassadors. Our goal in performing interviews at this stage is to inform intervention design and get feedback on study acceptability. Secondarily, we will be conducting interviews after the full pilot RCT, with up to 30 study participants. To gain diverse perspectives among study participants, we will aim to interview both male and female participants who completed the study. These interviews will be conducted in either English or Xhosa, last approximately 60 minutes and will be digitally recorded and transcribed. The purpose of interviews will be to further understand challenges and facilitators of each intervention component from the perspective of those who received and delivered the intervention. Themes of the interviews will include: a) barriers to participation and attendance; b) barriers to MI protocol; c) relevance of peer-support, d) relevance of peer navigation; e) interaction between program participation and clinic attendance; f) unanticipated problems with the control condition. Among staff, we will also ask about issues related to study recruitment, participation and retention.

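### The interviews after the randomized pilot aim at study completers, so intervention-arm participants who withdrew or were lost are not targeted (low priority, cheap to improve)

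*Combined protocol and SAP*

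**What the plan says.** The section on process evaluation (feasibility and acceptability) plans in-depth interviews at two points.

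- **After the open, non-randomized pilot**, the team will "interview all 10 participants (all of whom received the pilot intervention) and the Treatment Ambassadors". No completion condition is attached.
- **After the randomized pilot**, up to 30 participants will be interviewed. The sampling sentence begins "To gain diverse perspectives among study participants" and continues "we will aim to interview both male and female participants who completed the study". No other selection criterion is given.

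The stated purpose is to understand what helped and hindered each component "from the perspective of those who received and delivered the intervention". The first of six themes is "a) barriers to participation and attendance".

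The same section names other sources that touch on dropout:

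- "Attendance registers to provide data on enrollment, dropout and attendance of the intervention", completed by intervention staff;
- "The RA will document challenges in both the intervention and control conditions", where RA is the research assistant and the notes include participants' reactions;
- "Among staff, we will also ask about issues related to study recruitment, participation and retention".

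Elsewhere, the peer-support description has all Treatment Ambassador contacts logged, and the fidelity text has every session recorded. The Data Collection text treats the six-month survey as the end of the study and encourages those who leave the program to keep completing surveys. The primary-analysis paragraph says assessment will continue after a participant stops treatment.

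**The concern.** The sampling sentence seeks varied perspectives, and one theme is why people do not take part or attend. Yet its aim is limited to people who stayed to the end. TAP participants who attended some sessions and then left the study also received part of the intervention. They are well placed to say why it did not suit them. The open-pilot interviews carry no such condition, and no reason is given for adding it in the randomized phase.

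This matters because the protocol makes acceptability and feasibility the focus of this phase, and barriers and facilitators from the process evaluation drive revision of the manual. If the aim is followed, the in-depth interviews of randomized participants will contain no first-hand account from those who left.

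**Working it through.** **1. Who falls inside and outside the aim**

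| Group in the TAP arm | Position under the stated aim |
|---|---|
| Attended sessions and finished follow-up | Inside |
| Stopped or rarely attended sessions, finished follow-up | Inside (completion is tied to the six-month survey, not to attendance), but not targeted |
| Withdrew from the study or lost before six months | Outside |

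**2. Do other sources record leavers' own reasons?**

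| Source | What it gives | Leavers' own reasons for leaving? |
|---|---|---|
| Attendance registers | Staff record of enrolment, dropout, attendance | Reasons not mentioned |
| RA notes and weekly minutes | Staff account of reactions and difficulties | Second-hand |
| Logged contacts, recorded sessions | Barriers voiced while still engaged | Before leaving, not exit reasons |
| Staff interviews | Staff view of retention | Second-hand |
| Surveys | Program dropouts encouraged to complete them | No such item described; items not reproduced |
| Open-pilot interviews | All 10 pilot participants | Not randomized-phase participants |

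None is described as obtaining randomized leavers' own reasons. This statement covers the available text only.

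**3. How many people are concerned**

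Inputs from Power/Sample Size Considerations: up to 90 recruited, 45 per group, attrition not above 10%, complete sample of 80.

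- Reproducing the plan's figure: 40 / (1 − 0.10) = 44.4, rounded up to 45 per group, or 90 in total. It reproduces.
- TAP leavers at the ceiling, equal split by arm assumed: 45 × 0.10 = 4.5, so 4 to 5.
- At half the ceiling (assumed): 45 × 0.05 = 2.25, so 2 to 3.

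**4. What inviting them could yield**

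With K leavers all invited and response probability r (assumed, independent), expected interviews = K × r, and the chance of at least one = 1 − (1 − r)^K.

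| r | K = 4 | K = 5 |
|---|---|---|
| 10% | 0.4; 1 − 0.9⁴ = 34% | 0.5; 1 − 0.9⁵ = 41% |
| 20% | 0.8; 1 − 0.8⁴ = 59% | 1.0; 1 − 0.8⁵ = 67% |
| 50% | 2.0; 1 − 0.5⁴ = 94% | 2.5; 1 − 0.5⁵ = 97% |

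At half the ceiling with r = 50%: 1.0 to 1.5 interviews, with a 75% (1 − 0.5²) to 88% (1 − 0.5³) chance of any. Under the stated aim, if followed, the number is 0.

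**The case against.** The strongest reply is that little is lost.

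- **The wording is an aim, and completion is tied to the six-month survey.** People who rejected the sessions but stayed in follow-up can be interviewed about attendance, and they may be the most informative group on acceptability. This stands. A reader might infer that program dropouts are barred from the interviews; the text does not say so.
- **The phrase may mainly mark timing**, since these interviews follow the trial, with gender balance as the real intent. That reading is possible. However, the sentence is the only selection statement, and taken as written it directs staff to completers.
- **Other sources narrow the gap.** This stands in part. A reader might infer that the plan learns nothing about dropout; the registers, notes, contact logs, recordings and staff interviews contradict that. What they are not described as giving is the leaver's own account of leaving.
- **The claim that nothing plans to obtain leavers' reasons is a negative one.** Survey items, interview guides and register forms are not in the available text, so it is limited accordingly.
- **Leavers are few and hard to reach, and some exercised a right to withdraw.** This stands and limits the gain. Choosing interviewees from those reachable at the end is a defensible choice for a pilot.

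**Conclusion.** The point holds as a cheap, low-priority improvement. The stated aim leaves out TAP participants who withdrew or were lost, and in the available text no other source is planned to collect their own reasons. The group is about 4 to 5 of 45. That figure rests on the protocol's 10% ceiling and an assumed equal split by arm; the documents give no split, and actual attrition may differ.

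A reader might go further and conclude that the interview findings will be biased in the program's favour. A favourable lean is plausible, but nothing in the documents shows it, and manual revision draws on all process-evaluation sources. Initiation of antiretroviral therapy, the primary outcome, and its analysis are untouched.

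**What to change.** In the in-depth interview paragraph, delete the last four words of "we will aim to interview both male and female participants who completed the study". Keep the cap of 30. Select purposively by TAP session attendance (from the existing registers) and by follow-up status, as well as by gender. Invite participants who left only where their consent allows it, and reallocate any unfilled slots. If no leaver is interviewed, report the interview findings as completers' views.

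The cost is tracing a handful of people and possibly some consent wording, because participants may withdraw at any time (Potential Risks, Special issue #1, and the psychological distress section). No new data system or extra interviews are needed. The reporting caveat costs nothing and is worth adopting even if tracing fails.
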